4.9 Study closure

We aimed to recruit approximately 250 participants in total (at least 62 patients and 47 partners per phase) with a minimum study duration of two years. The end of the study will be following the analysis of the patients' questionnaires.

However, in light of the SARS-CoV-2 pandemic, partners cannot attend early pregnancy units. It is likely that data from patients only will be possible to be collected as we will not be able to make up the difference regarding partners as patient recruitment is already under way. The total we will be able to recruit will therefore be at least 124 (at least 62 patients per phase). Although this reduces the scope of the study, we will still be able to meet the vast majority of our objectives.

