4.6 Withdrawal criteria

Patients and/or their partners may withdraw from the study at any stage and all data captured in relation to their participation may be destroyed at their request.

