Patients and partners will be asked to complete the questionnaire at three time points: 1) On classification of PUL at time zero once blood is taken, 2) at the 48-hour time point after blood is taken (if 48-hour bloods are required for the patient); and 3) after definitive diagnosis and management.

The maximum number of questionnaires that will be completed will be 6: 1 for each time point for the patient and 1 for each time point for the partner.

The questionnaires for the first two time points will be offered electronically whilst the patient is having their blood sample taken via use of a quick response matrix barcode (QR code). The third time point HADS will be texted through the encrypted system Accurx. We will contact the patient a maximum of 3 times to complete the questionnaire at the third time point to reduce loss of follow up.

The results will be submitted electronically each time. The results will be reviewed on a weekly-biweekly basis by the research team.

If patients score for moderate to severe anxiety or depression at any time point, we will call the patient. If they are struggling with their PUL classification or diagnosis, we will advise them to make an appointment to see their GP as soon as possible to arrange appropriate follow up, whilst clarifying any ongoing follow up at the early pregnancy unit. If patients score for moderate to severe anxiety or depression at any time point where no further follow up at the unit is indicated, we will also ask permission to send a text over Accurx that will list information relating to local miscarriage support groups, Tommy's Miscarriage charity, Petals Baby Loss Counselling Charity, the Ectopic Pregnancy Trust, the Miscarriage Association and Improving Access to Psychological Therapists (IAPT). If further support is required, they will be advised to contact their GP as soon as possible.

a. Symptoms

Patients will be asked to complete the standard clerking proforma used within the unit, including demographic data and information regarding previous obstetric, medical and gynaecological history and questions regarding symptoms.

b. Ultrasound

Trans-vaginal ultrasound is then performed as part of standard practice. Women with a PUL will be identified as eligible for the study

Any ultrasound abnormality detected will be managed in accordance with local and national guidance. Follow up trans-vaginal ultrasound for all will be arranged as per routine clinical practice if required.

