6.1 Statistics and data analysis

Recruitment will commence upon ethical approval of the study. The infrastructure, research fellow and nurses, questionnaires, BhCG machines and database are already in place, which ensure that the study can start promptly upon approval, without affecting or compromising routine clinical service provision. We aim to recruit 250 participants. As the early pregnancy unit assesses approximately 4200 women per annum, this aim is achievable over the course of two years. We will also be recruiting in two centres within Imperial College Healthcare NHS Trust to ensure there is generalizability in the results.

The calculated sample size follows from the pilot study performed by Farren et al [21] as well as the associated study focussing on partners [24]. Data from the pilot study suggests that 32% of those suffering early pregnancy complications had moderate to severe anxiety compared with 10% in the control group [21]. As this will initially be performed as a pilot study, at least 62 women will be required in both phase 1 and phase 2 where recruitment ratio is 1:1 with type 1 error of 0.05 and power of 80% [25]. Data from the partner study highlighted that the 30% of women reported moderate to severe anxiety compared with 6% of partners [24]. Again, as this will be performed as a pilot study, at least 47 partners will be required in both phase 1 and phase 2 where recruitment ratio is 1:1, with type 1 error of 0.05 and power of 80% [25]. However, due to the SARS-CoV-2 pandemic, it is likely we will only be able to assess patients and not partners.

7. Study Supervision and Monitoring

a. Risk assessment

In summary, there is no significant increase in time spent within the unit or of risk of complications to the patient:

- Trans-vaginal ultrasound is performed routinely in EPU and so does not add to the burden or risk of the patient;
- All research blood samples will be taken/arranged for patients who attend routine EPU appointments only or following admission to the gynaecology ward. All blood samples will therefore be taken at the same time as blood taken as part of routine clinical care, preventing risk and burden as no further venepuncture will be required. These will be taken by highly skilled and trained clinical fellows and research midwives who are medically trained in phlebotomy, reducing potential for discomfort;

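### The 62 women per phase needed for 80% power is also the recruitment minimum, so the stated power has no allowance for missing questionnaires after time zero

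*Combined protocol and SAP*

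**What the plan says.** Section 6.1 (Statistics and data analysis) takes its rates from an earlier study in the unit, in which "32% of those suffering early pregnancy complications had moderate to severe anxiety compared with 10% in the control group". From these, with a type 1 error of 0.05, power of 80% and equal recruitment to the phases, it concludes that "at least 62 women will be required in both phase 1 and phase 2". It describes the work as initially a pilot. It names no test for the phase comparison and no time point to which the power applies.

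The section headed Study closure (one of two numbered 4.9) explains that partners probably cannot be recruited because of the pandemic, and gives a revised total: "The total we will be able to recruit will therefore be at least 124 (at least 62 patients per phase".

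Neither section mentions missing data. Three other provisions bear on how many women will have a questionnaire to analyse:

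- The third HADS is sent by text message after diagnosis and management. Under Method of study (the other section 4.9), women are contacted up to three times "to complete the questionnaire at the third time point to reduce loss of follow up".
- The same section offers the 48-hour HADS only to women who need 48-hour bloods.
- Section 4.6 lets participants withdraw at any stage, in which case "all data captured in relation to their participation may be destroyed at their request".

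**The concern.** A sample size from a power formula counts the people who enter the analysis. If the same number is the recruitment minimum, the stated power is reached at that minimum only if every woman recruited has a usable questionnaire at the time point compared. The plan does not expect that at the third HADS, and by design not every woman need complete the 48-hour HADS.

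Hypothesis 2, that faster results reduce anxiety and depression, rests on comparing the two phases. If that comparison shows no difference, readers will weigh it against the 80% in section 6.1. If fewer women were analysed than the calculation assumed, a null result would look more informative than it is.

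**Working it through.** **Inputs.** From section 6.1: p1 = 0.32, p2 = 0.10, type 1 error 0.05, power 80%, ratio 1:1. Sidedness is not stated; two-sided is assumed because it reproduces the plan's figure. Loss rates are assumed, because the documents give none.

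**Step 1: reproduce 62.** With d = 0.22 and mean proportion p̄ = 0.21, the uncorrected number per phase is

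n = [1.960·√(2p̄(1−p̄)) + 0.842·√(p1(1−p1) + p2(1−p2))]² / d²

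= (1.129 + 0.467)² / 0.0484 = 52.6, so 53.

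The continuity-corrected number is

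n′ = (n/4)·[1 + √(1 + 4/(n·d))]²

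= (52.6/4)·[1 + √1.346]² = 61.4, so 62.

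This matches the plan. The partner figure confirms the method: 30% v 6% gives 46.99 corrected, matching the plan's 47, and 39.03 (so 40) uncorrected, which does not match. For 32% v 10%, one-sided versions give 42 uncorrected and 51 corrected. So 62 is the corrected number itself, not a smaller number with an allowance added.

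**Step 2: power when fewer than 62 are analysed.** On the plan's corrected basis,

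power = Φ{[(d − 1/n)·√n − 1.129] / 0.5546}, where 0.5546 = √(p1(1−p1) + p2(1−p2)).

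- n = 62: (1.605 − 1.129)/0.5546 = 0.859, so 80.5%.
- n = 50: (1.414 − 1.129)/0.5546 = 0.514, so 69.6%.

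The table adds Fisher's exact test and the uncorrected chi-square test. The chi-square test is shown by exact enumeration of the two binomial distributions and by the normal approximation. Numbers analysed are 62 × (1 − loss), to the nearest whole woman.

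| Analysed per phase | Corrected formula | Fisher exact | Chi-square, exact enumeration | Chi-square, normal approximation |
|---|---|---|---|---|
| 62 (no loss) | 80.5% | 82.1% | 86.9% | 86.2% |
| 56 (10%) | 75.5% | 77.2% | 84.3% | 82.5% |
| 53 (15%) | 72.7% | 75.5% | 82.1% | 80.3% |
| 50 (20%) | 69.6% | 72.1% | 80.0% | 77.9% |

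**Step 3: where 80% is lost.** On the corrected formula, 61 analysed gives 79.7%, so one loss per phase is enough. For the uncorrected test, the normal approximation holds 80% down to 53 analysed (9/62 = 14.5% lost). Exact enumeration gives 79.97% at 50 (12/62 = 19.4% lost).

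**Step 4: look for an allowance elsewhere.** The earlier target of about 250 exceeds 2 × (62 + 47) = 218 by 32. The plan does not call those 32 a dropout allowance or divide them between women and partners. The revised total is 2 × 62 = 124, with nothing over.

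**The case against.** Much of the case on the other side stands.

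- **No test is named.** The formula used to size a study need not be the test used to analyse it. With an uncorrected chi-square test, 62 recruited keeps about 80% power through 15–19% loss. This is the strongest objection. It makes the shortfall conditional, but the plan cannot claim that margin without naming the test.
- **62 is a floor.** Both sections say at least. The phases have only minimum durations, section 6.1 still carries the aim of 250 participants, and the unit sees about 4,200 women a year. Over-recruitment could absorb the loss. None is planned, though, and the 80% is tied to the floor.
- **The evidence for loss is uneven.** The first two questionnaires are offered by QR code while blood is taken, so time zero should lose little. The 48-hour restriction defines a subset and is not loss to follow-up, although it lowers the number analysed all the same. The withdrawal clause is a right and predicts nothing. Only the text on the third HADS shows that loss is anticipated, and there the plan tries to limit it.
- **It is a pilot.** True, but section 6.1 still states a formal 80%.
- **The effect size is the larger question.** The 32% v 10% contrast is between women with complications and controls. It says nothing about how far point-of-care testing might lower anxiety between phases. This is right, and it limits every power figure given here.

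A reader might go further and infer that the study will fall short of 80% power, or that the sample size is miscalculated. The documents support neither. They give no loss rate, test or time point from which a shortfall could be established, and the calculation reproduces exactly.

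**Conclusion.** The point holds as an omitted allowance. The number required and the minimum recruited are the same 62 per phase, and 62 contains no margin on the basis used to derive it. At the 48-hour and third questionnaires, fewer than 62 per phase are likely to be analysed unless recruitment passes the minimum.

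For assumed losses of 10% to 20%, power is 75.5% to 69.6% on the plan's corrected basis, 77.2% to 72.1% with Fisher's exact test, and 84.3% to 80.0% with an uncorrected chi-square test. The conclusion is therefore that 80% should not be stated without conditions, not that it will be missed.

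This rests on a two-sided 5% test, on loss rates assumed here, on recruitment at the minimum with equal loss in both phases, and on a true difference of 32% v 10%.

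**What to change.** Leave recruitment as it is and revise section 6.1:

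1. State that 62 per phase is the number of women with an analysable questionnaire.
2. Name the time point and the test to which the 80% applies.
3. Replace the unconditional 80% with the power from 62 recruited per phase at, for example, 10%, 15% and 20% missing, using the column of the table for the test chosen.
4. State that these figures hold only for a 32% v 10% difference, which came from women with complications v controls and not from phase 1 v phase 2.
5. Commit to reporting the number analysed in each phase at each time point.

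The cost is a few sentences, with no extra patients and no change in procedures. The downside is that, on the corrected or Fisher basis, the stated power becomes less favourable.

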4.10 Documentation and communication

Clinical data, patient demographics and ultrasound findings will be recorded on the standard clerking proforma filled in by each patient and on a computer software programme (Astraia). This data will be prospectively collated into a master database with raw data relevant to the study. All potential identifiable patient data that requires electronic storage will be stored electronically on NHS approved computers, accessible by members of the research team or the patients direct care team via secure password in the Early Pregnancy Unit, Queen Charlotte's & Chelsea Hospital, Imperial College Healthcare NHS Trust, Hammersmith Hospital. No patient identifiable information will leave the hospital premises nor be subject to access or viewing by anyone other than those directly involved with this research study. Data will be stored for a minimum of 10 years after completion of the study.

5. Study Outcome measures

Psychological morbidity will be assessed using the HADS on time of PUL classification, 48 hours from PUL classification and following final diagnosis and management.

6. Study population and sample size

6.1 Statistics and data analysis

Recruitment will commence upon ethical approval of the study. The infrastructure, research fellow and nurses, questionnaires, BhCG machines and database are already in place, which ensure that the study can start promptly upon approval, without affecting or compromising routine clinical service provision. We aim to recruit 250 participants. As the early pregnancy unit assesses approximately 4200 women per annum, this aim is achievable over the course of two years. We will also be recruiting in two centres within Imperial College Healthcare NHS Trust to ensure there is generalizability in the results.

The calculated sample size follows from the pilot study performed by Farren et al [21] as well as the associated study focussing on partners [24]. Data from the pilot study suggests that 32% of those suffering early pregnancy complications had moderate to severe anxiety compared with 10% in the control group [21]. As this will initially be performed as a pilot study, at least 62 women will be required in both phase 1 and phase 2 where recruitment ratio is 1:1 with type 1 error of 0.05 and power of 80% [25]. Data from the partner study highlighted that the 30% of women reported moderate to severe anxiety compared with 6% of partners [24]. Again, as this will be performed as a pilot study, at least 47 partners will be required in both phase 1 and phase 2 where recruitment ratio is 1:1, with type 1 error of 0.05 and power of 80% [25]. However, due to the SARS-CoV-2 pandemic, it is likely we will only be able to assess patients and not partners.

7. Study Supervision and Monitoring

a. Risk assessment

In summary, there is no significant increase in time spent within the unit or of risk of complications to the patient:

- Trans-vaginal ultrasound is performed routinely in EPU and so does not add to the burden or risk of the patient;
- All research blood samples will be taken/arranged for patients who attend routine EPU appointments only or following admission to the gynaecology ward. All blood samples will therefore be taken at the same time as blood taken as part of routine clinical care, preventing risk and burden as no further venepuncture will be required. These will be taken by highly skilled and trained clinical fellows and research midwives who are medically trained in phlebotomy, reducing potential for discomfort;

Taking part in the study will allow the assessment of the psychological impact of pregnancy of unknown location (PUL) classification pending a final diagnosis. It will also allow the assessment of psychological burden of PUL on their partners. Finally, we hope to establish if shortening time to providing patients classified with PUL with results and advice using pointof-care BhCG testing reduces psychological burden.

The results will not impact patient care negatively, and we in fact hope patients in the future will benefit from the information gained in this study.

b. Central and local supervision

The chief investigator at Imperial College London will be responsible for the protocol, quality control, interim analyses of the data, advice on progress and final analysis and reporting of the study.

8. Regulatory Issues

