2.2 Study rationale and study hypothesis

a. Study rationale

PUL is a syndrome of early pregnancy composed of a positive urine pregnancy test without the visualisation of a pregnancy on trans-vaginal ultrasound (TVUS). The current method for risk stratifying a PUL is via serum BhCG levels at the time of identification of PUL and after 48 hours, in order to ascertain the viability of the pregnancy. Patients and their partners need to wait for this result before a management plan can be adopted, taking at least 2-3 hours.

There is a clear need for the patient care pathway to evolve in order to aid and improve the management of women classified with a PUL. By using point-of-care BhCG testing, we would shorten the time to management. We propose that shortening the time interval would reduce psychological morbidity.

b. Study hypothesis

- 1) PUL causes significant psychological distress to patients and their partners which can be assessed using a validated psychological tool.
- 2) Increasing the efficiency of PUL management will reduce anxiety and depression symptoms in patients and their partners.

3. Study Objectives

This study aims to improve the pathway of care to this cohort of women by:

- Assessing the psychological impact of pregnancy of unknown location (PUL) classification pending a final diagnosis.
- Assessing psychological burden of PUL on patients and their partners.

· Assessing if shortening time to providing patients classified with PUL with results and advice using point-of-care beta human chorionic gonadotrophin (BhCG) testing reduces psychological burden.

4. Methodology and Design

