4.2 Design and links to previous studies

a. Design

SOUL is prospective cohort observational study focussing on psychological assessment of patients and their partners with PUL.

b. Links to previous studies

Pilot study undertaken in the unit in 2016 by Farren J et al [21], led by Chief Investigator [name], explored the severity and type of emotional distress in women after early pregnancy loss compared with women with ongoing pregnancies (REC 11/SW/0052). This group implemented HADS.

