4.9 Method of study

This is a cohort study and will recruit patients in the first trimester (less than 14 weeks gestation) and their partners who meet the inclusion criteria attending the Early Pregnancy Unit. There will be two phases of the study, each with a minimum duration of 4 months. Phase 1 aims to establish the psychological burden of PUL under the existing care pathway, whilst phase 2 introduces point of care BhCG testing in clinical practice. The phases of the study are described in more detail below.

An information leaflet detailing the purpose of the study will be provided, and separate patient information sheets will be used for each phase of the study. A minimum of 15 minutes will be provided for patients to read the study information with the research team not present. Patients will then have opportunity to elicit further information or clarification from the research team. There are no significant ethical, legal or management issues. Women who both verbally consent and consent in writing will follow a well-defined pathway (see flowchart appendix).

The phases of the study are

- Group 1: Assessing the psychological impact of pregnancy of unknown location (PUL) classification pending a final diagnosis. Confirming the reliability of point of care testing in correlation with laboratory BhCG levels (gold standard).
- Group 2: To assess if shortening time to providing patients classified with PUL with results and advice using point-of-care beta human chorionic gonadotrophin (BhCG) testing reduces psychological burden.

Women with symptoms in the first trimester are routinely seen in the Early Pregnancy Unit (EPU). A clerking proforma is completed, urine is tested and a transvaginal ultrasound scan is performed. Blood testing and follow up arrangements are made if required with blood results inputted into a validated statistical model if a patient is classified with a PUL.

Participants in phase one of the study will not be provided with the POC BhCG result. They will await the laboratory result. Simultaneously we will ascertain reliability of POC in clinical practice during this time.

Patients in phase two will be provided with the POC test result, which will reduce the time to which they receive the result. Prior to transfer from phase 1 to phase 2 of research, correlation between POC and laboratory BhCG levels will be calculated in order to confirm its reliability by creating a correlation curve using the data.

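### The 62 women per phase are sized on 32% v 10% against an external control group; for phase 1 v phase 2 the stated 80% power requires anxiety to fall from 32% to about 10–12%

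*Combined protocol and SAP*

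**What the plan says.** Section 6.1 (Statistics and data analysis) holds the only sample size justification. It cites a pilot study in which "32% of those suffering early pregnancy complications had moderate to severe anxiety compared with 10% in the control group" and then states that "at least 62 women will be required in both phase 1 and phase 2", with 1:1 recruitment, type 1 error 0.05 and power 80%. Section 4.2 describes that pilot as studying women after early pregnancy loss "compared with women with ongoing pregnancies".

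The phases are defined in section 4.9 (Method of study). "Participants in phase one of the study will not be provided with the POC BhCG result"; they wait for the laboratory value. "Patients in phase two will be provided with the POC test result", which shortens the wait. Both phases recruit women with PUL. Section 2.2 b gives the hypothesis that this comparison serves: "Increasing the efficiency of PUL management will reduce anxiety and depression symptoms in patients and their partners". No section gives an expected phase 2 rate or a target reduction.

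Three related statements matter less:
- Section 6.1 sets 47 partners per phase, also at 80% power, from 30% of women v 6% of partners.
- Section 4.9 (Method of study) limits contact attempts "to complete the questionnaire at the third time point to reduce loss of follow up" and takes the second questionnaire only "if 48-hour bloods are required for the patient". Section 6.1 makes no allowance for missing questionnaires.
- Section 6.1 still aims for 250 participants, whereas section 4.9 (Study closure) now gives a minimum of 124.

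**The concern.** A power statement describes a particular contrast. The contrast behind the 62 is complicated pregnancy v ongoing pregnancy. The contrast to which the 62 is applied is laboratory result v point-of-care result, both among women with PUL. Carrying 32% v 10% across to the phases assumes that a faster blood result closes nearly the whole gap between women with early pregnancy complications and the control group. The plan does not state that assumption or argue for it.

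The second hypothesis is at stake. A reader of section 6.1 will take it that the study has 80% power to show whether point-of-care testing helps. If the true benefit is smaller than about 20 percentage points, a non-significant phase comparison is a likely result even though the benefit is real. The plan gives no warning against reading that as no benefit.

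**Working it through.** **Inputs.** From section 6.1: p1 = 0.32, p2 = 0.10, 1:1 recruitment, type 1 error 0.05, power 0.80, n = 62 per phase. Sidedness and test are not stated. Two-sided testing is assumed because, with the continuity correction, it reproduces the plan's figures. The phase 1 rate is taken as 32%, the plan's own input; the documents give no rate specific to PUL.

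**Step 1: reproduce the plan's figures.** With d = p1 − p2 and p̄ = (p1 + p2)/2:

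- n = [1.960·√(2p̄(1−p̄)) + 0.842·√(p1(1−p1) + p2(1−p2))]² / d²
- with continuity correction: n′ = (n/4)·[1 + √(1 + 4/(n·d))]²

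For 32% v 10%, p̄ = 0.21 and d = 0.22. Then n = (1.129 + 0.467)²/0.0484 = 52.6 and n′ = 61.4, which rounds up to **62**. For 30% v 6%, n = 39.03 and n′ = 46.99, which rounds up to **47**. Both stated figures therefore come from the borrowed contrasts.

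**Step 2: power of the phase comparison at 62 v 62.** Exact power sums the product of the two binomial probabilities over every pair of counts that the test calls significant (two-sided 5%). Phase 1 is 32%.

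| Phase 2 rate | Yates-corrected | Uncorrected chi-square |
|---|---|---|
| 10% | 82% | 87% |
| 11% | 77% | 83% |
| 12% | 71% | 78% |
| 16% (halved) | 47% | 55% |
| 20% | 26% | 33% |
| 24% | 12% | 17% |

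Power equals 80% at a phase 2 rate of 10.4% (Yates) or 11.6% (uncorrected). That is an absolute fall of 32 − 11.6 = 20.4 to 32 − 10.4 = 21.6 points, about two thirds of the starting rate. A true halving would be missed 45–53% of the time.

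**Step 3: number needed for smaller falls.** By the step 1 formula, without and with the correction, 80% power needs 111 or 123 per phase for 32% v 16%, and 209 or 225 for 32% v 20%.

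**Step 4: precision.** The expected 95% CI half-width is 1.96·√[(p1(1−p1) + p2(1−p2))/62]. It is 13.8 points for 32% v 10%, 14.8 for v 16%, 15.3 for v 20% and 15.7 for v 24%. For 32% v 20% the expected interval is 12 ± 15.3, about −3 to +27 points.

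**Step 5: sensitivity to the phase 1 rate.** Because 32% is itself borrowed, the phase 1 rate was varied. The 18% is the lower end of the 18–32% anxiety range in section 2.1 d; 25%, 40% and 50% are assumptions.

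| Phase 1 rate | Phase 2 rate giving 80% power | Power if anxiety halves |
|---|---|---|
| 18% | 2–3% | 23–30% |
| 25% | 6–7% | 35–42% |
| 32% | 10–12% | 47–55% |
| 40% | 16–18% | 62–69% |
| 50% | 25–26% | 78–83% |

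**Step 6: the lesser points.** If only 54 or 50 women per phase were analysed (illustrative; no loss rate is given), power for 32% v 10% would be 75–83% or 72–80%. For partners at 47 per phase starting from 6%, even a fall to 0% has only 6–31% power, so no reduction reaches 80%.

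**The case against.** The best opposing case has four parts.

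- **The baseline is uncertain.** The 32% is no more a PUL rate than the 10% is a phase 2 rate. Section 2.1 d cites evidence that diagnostic uncertainty drives anxiety more than the diagnosis itself, so anxiety while waiting could be higher. From 50%, a halving would have about 80% power. This stands as a reason to show a range. It does not rescue the power statement, which uses 32%, and a lower baseline makes the position worse.
- **It is a secondary aim in a study called a pilot.** The primary aim is descriptive and needs no test between phases; 62 women estimate a 32% rate to within about ±12 points. The 62 is also a minimum. This is true and limits the damage to one hypothesis. But section 6.1 attaches 80% power and a 1:1 ratio to the two phases in the same sentence as the pilot label, and it offers no precision argument for the descriptive aim.
- **No analysis is fixed.** HADS scores could be compared as continuous measures, with different power. This stands as a limit on the figures above, but section 6.1 is built on the proportion with moderate to severe anxiety, and no score-based analysis is planned.
- **Nobody proposes to read a null result as no benefit.** This is correct, and the caution asked for is a safeguard rather than a correction. It is needed because the stated 80% invites that reading.

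The partner figure is largely moot, since sections 4.9 (Study closure) and 6.1 already expect no partner data.

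**Conclusion.** The concern holds. The 62 per phase is correctly computed, but for a contrast that SOUL does not make. Applied to phase 1 v phase 2, the stated 80% power requires moderate to severe anxiety to fall from 32% to about 10–12% or lower. For a halving the power is 47–55%, and for a fall to 20% it is 26–33%.

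These figures assume a 32% phase 1 rate, a two-sided 5% comparison of two proportions, and 62 analysed women in each phase. Missing questionnaires would lower the power. A higher phase 1 rate would raise the power for a given proportional fall, and a lower one would reduce it. Because this is the only justification of the sample size and it carries an explicit 80%, it must be corrected. The partner figure, the undefined 62 and the leftover 250 are secondary.

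**What to change.** Restate section 6.1; no added patients are needed.

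1. Say that 62 analysed women per phase give about 80% power only for a fall from 32% to about 10–12% or lower. State that both rates come from an earlier study, neither being a rate for PUL, and that the 10% is its control group. Give the power for smaller falls (16%: 47–55%; 20%: 26–33%) and show a range of phase 1 rates.
2. Report the phase comparison as an estimated difference with a 95% CI, and state that a non-significant result will not be taken as evidence of no benefit.
3. Define the 62 as analysable questionnaires, remove the 80% claim for partners by phase, and replace the 250 with the minimum of 124 from section 4.9 (Study closure).

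The cost is a change of wording and a less favourable power statement for the second hypothesis.

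### The 47 partners per phase are sized for women v partners (30% v 6%), so the stated 80% power does not carry over to phase 1 v phase 2 in partners

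*Combined protocol and SAP*

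**What the plan says.** Section 6.1 justifies the partner sample from an earlier study of women and their partners, in which "30% of women reported moderate to severe anxiety compared with 6% of partners". It then concludes that "at least 47 partners will be required in both phase 1 and phase 2 where recruitment ratio is 1:1, with type 1 error of 0.05"; the power given is 80%. It gives no expected partner rate for phase 2 and no between-phase difference for partners. It does not say whether the test is one- or two-sided, and it names no analysis test.

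The phases differ in care pathway: laboratory BhCG results in phase 1, point-of-care results in phase 2 (section 4.9, Method of study). Hypothesis 2, in sections 1 and 2.2, reads: "Increasing the efficiency of PUL management will reduce anxiety and depression symptoms in patients and their partners". Separately, sections 1 and 3 list an aim on the psychological burden of PUL on patients and their partners.

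Section 4.9 (Study closure) gives the target as "at least 62 patients and 47 partners per phase", in the past tense. It then says that partners cannot attend because of the pandemic and that the achievable total is at least 124 patients. Section 6.1 says only that partner assessment is likely to be impossible. It keeps the 47, the 80% and the target of 250 participants.

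**The concern.** A sample size stated per phase, at 1:1, with a type 1 error and a power, reads as the size for comparing the phases. In partners that comparison is the test of hypothesis 2. The rates behind the 47, however, compare two kinds of participant, not two care pathways. The 24-point difference used for sizing is the gap between women and partners. From a 6% partner rate, the largest possible fall on this endpoint is 6 points.

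If partners were recruited and the phases did not differ significantly, a reader relying on the stated 80% could take the result as evidence that point-of-care testing does not help partners. The design could not support that conclusion on this endpoint at a 6% rate.

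**Working it through.** **Inputs, all from section 6.1:** type 1 error 0.05; power 80%; ratio 1:1; 30% (women) and 6% (partners); 47 partners per phase. For a cross-check of the method: 32% and 10%, giving 62 women per phase. Two-sided testing is inferred, because only that reproduces the plan's figures.

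**Step 1: reproduce the 47.** With d = p1 − p2 and p̄ the mean of the two rates:

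- n = [1.960 √(2p̄(1−p̄)) + 0.842 √(p1(1−p1) + p2(1−p2))]² / d²
- continuity-corrected n′ = (n/4)[1 + √(1 + 4/(n d))]²

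For 30% v 6%, p̄ = 0.18 and d = 0.24:

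- n = [1.960 × √0.2952 + 0.842 × √0.2664]² / 0.0576 = (1.065 + 0.434)² / 0.0576 = 39.0
- n′ = (39.0/4) × [1 + √(1 + 4/9.37)]² = 46.99, so 47

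The same formula for 32% v 10% gives n = 52.6 and n′ = 61.4, so 62, matching the women's figure. Other variants for 30% v 6% do not give 47: two-sided uncorrected 40, one-sided 31 or 39 (corrected), unpooled 37, arcsine 36. The 47 is therefore the size per group for women v partners.

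**Step 2: power of 47 v 47 for the contrast it was built on.** Exact binomial enumeration for 30% v 6%, groups treated as independent, gives 82.5% (Fisher) and 90.1% (uncorrected chi-square). With the planned 62 women and 47 partners in one phase it is 87.5% (corrected). The 80% is sound for this contrast.

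**Step 3: power of 47 v 47 for phase 1 v phase 2 in partners.** Assume that phase 1 partners have the plan's 6% rate. Expected cases in phase 1 are 47 × 0.06 = 2.8. Take the most favourable case, a fall to 0%, so that phase 2 has no cases. Power is then the chance that phase 1 has enough cases for significance:

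- Fisher: 5 v 0 gives two-sided p = 2 × (47·46·45·44·43)/(94·93·92·91·90) = 0.056, not significant. 6 v 0 gives 0.056 × 42/89 = 0.026. So at least 6 cases are needed, and the continuity-corrected chi-square needs the same number. P(X ≥ 6 | 47, 0.06) = 6.1%.
- Uncorrected chi-square: 3 v 0 gives z = 1.76; 4 v 0 gives z = 2.04. So at least 4 cases are needed. P(X ≥ 4 | 47, 0.06) = 31.1%.
- Normal approximation, uncorrected: Φ[(0.06√47 − 1.960√0.0582)/√0.0564] = Φ(−0.26) = 39.8%.

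| Partners, 47 v 47, two-sided 0.05 | Fisher or corrected | Uncorrected, exact | Normal approximation |
|---|---|---|---|
| 6% v 0% | 6.1% | 31.1% | 39.8% |
| 6% v 3% (illustrative halving) | 1.7% | 10.0% | 10.4% |

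A one-sided uncorrected test, which does not match the plan's sizing, would have 54% power for 6% v 0%, still below 80%.

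**Step 4: scale.** The plan's own formula needs 158 partners per phase for 80% power at 6% v 0% (126 uncorrected). Conversely, at 47 per phase, 80% power for a fall to zero needs a phase 1 partner rate of about 15% (uncorrected normal approximation).

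**The case against.** Four points on the other side have substance.

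- **The 47 has a legitimate reading.** It suits women v partners within each phase, which matches the aim on burden in patients and partners. The statement of the point-of-care aim mentions only patients; hypothesis 2 alone brings partners into the between-phase question. This stands: the figure is not miscalculated, and the 80% should be re-attached, not simply struck out. It does not remove the mismatch, because hypothesis 2 is still in the plan and 6.1 never says which contrast is powered.
- **The power depends on the test, the endpoint and the rate.** A reader might infer that an effect in partners could almost never be detected, or that no effect, however large, could reach 80%. The documents do not support either. No test is named, and at 31% to 40% power the first is false. The second holds only for the dichotomised anxiety endpoint at 6%. Hypothesis 2 speaks of symptoms, and the HADS gives scores of 0 to 21 per subscale, for which the 6% floor does not bind. The 6% comes from a study of miscarriage and ectopic pregnancy, so the rate among partners in PUL is unknown.
- **Partners will probably not be recruited, and the plan calls this a pilot.** This limits the practical weight. It does not settle the matter, because 6.1 keeps the 47, the 80% and the 250.
- **A reader might infer that 47 partners in total, over both phases, would be enough for women v partners.** That would require independent groups although couples are paired, pooling of two care pathways, and no loss to follow-up. The plan establishes none of these, and it provides for up to three contacts to limit loss at the third questionnaire.

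**Conclusion.** The point holds as a mismatch between a sample size and a hypothesis, not as an arithmetic error. The 47 with 80% power belongs to women v partners at 30% v 6%. It does not support the partner part of hypothesis 2. For phase 1 v phase 2 in partners, power is about 6% to 40%, depending on the test, even for a fall from 6% to 0%. This rests on a 6% phase 1 partner rate, the moderate to severe anxiety endpoint, two-sided 0.05, independent groups and no loss to follow-up. The correction is worth making because the text is still in force and the change is cheap. Its consequence is modest while partners are not expected to take part.

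**What to change.** In section 6.1:

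- State that 47 with 80% power refers to women v partners (30% v 6% moderate to severe anxiety), two-sided 0.05 with continuity correction, groups treated as independent and no allowance for loss to follow-up.
- Remove the implication that it powers phase 1 v phase 2 in partners.
- Add that, if partners are recruited, the between-phase comparison in partners is descriptive (difference with 95% CI), with about 6% to 40% power, depending on the test, for 6% v 0%.

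Limit the partner part of hypothesis 2 to match, in both sections 1 and 2.2, and align section 4.9 (Study closure). Do not write that 47 partners in total are enough.

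The cost is a wording change in these places. No extra recruitment is needed. The downside is a less favourable stated power for partners.
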